Completing the online screening and consent procedure will take 5-15 minutes.

Describe how the data will be collected (i.e. in person or online).

Online

Will any video, photography, or audio be recorded as part of this procedure?

No

Will data be collected anonymously?

No

Procedure Description

Participation in the Mentoring Program

This procedure is:

Research Activity Involving Participants, Participants Data, or Biospecimens

This procedure is:

Where and when will this procedure take place?

Program facilitation will be conducted by trained staff members ([name], [name]) through WCNC – either in-person at clinic facilities or virtually by Zoom depending on health guidelines. Programs will start running in August, 2021, with a new group starting each month.

Who will conduct this procedure?

Personnel

[name]

External User

Personnel

[name]

External User

Indicate the frequency and duration of visits/sessions as well as the subject's total time commitment for the study.

1.5 hours per session, with 8 total sessions. Total time: 12 hours.

Describe how the data will be collected (i.e. in person or online).

Facilitators will be asked to keep attendance data, rate participant engagement, and complete a checklist of program items completed for each week of the intervention. At the end of the mentoring program, facilitators will also be asked to provide their feedback about the supportiveness of the group dynamics.

Will any video, photography, or audio be recorded as part of this procedure?

No

Will data be collected anonymously?

No

Procedure Description

Online Surveys

This procedure is:

Research Activity Involving Participants, Participants Data, or Biospecimens

This procedure is:

Experimental

Where and when will this procedure take place?

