Participants from the mentoring group or who are on a waiting list for the next mentoring group will be invited to complete electronic surveys at four time points over four months, with four weeks between each survey. A WCNC staff member ([name]) will send out a survey link to consented participants at each time point. Surveys will be available through [name]'s CSU Qualtrics account. Participants will enter their unique ID number in each survey so surveys can be linked over time. Surveys will assess demographics and outcomes of interest, including stress, mental health symptoms, parenting knowledge, confidence in parenting, the coparenting relationship, and satisfaction with their social networks. Participants will also be asked about whether or not they listened to podcasts.

Who will conduct this procedure?

Personnel

[name]

Personnel
[name]

External User

Indicate the frequency and duration of visits/sessions as well as the subject's total time commitment for the study.

15-30 minutes for each electronic outcome survey over 4 surveys. Total time: 1-2 hours.

Describe how the data will be collected (i.e. in person or online).

Online through Qualtrics

Will any video, photography, or audio be recorded as part of this procedure?

No

Will data be collected anonymously?

No

Procedure Description
Mentoring Program Satisfaction Surveys

This procedure is:

Research Activity Involving Participants, Participants Data, or Biospecimens

This procedure is:

Experimental

Where and when will this procedure take place?

Participants who have attended the mentoring program will be invited to complete an electronic satisfaction survey through [name]'s CSU Qualtrics account following completion of the group program. Surveys will ask about demographics, what participants liked or didn't like about the program, their perceptions of the group environment, and supportive group dynamics. Participants will also be given a brief (1-2 minute) electronic questionnaire at the beginning of each week of the program assessing their engagement in homework. Survey links will be sent by a member of the WCNC staff ([name]) to maintain separation of participant contact information from data. [name] will manage the data on the research side.

Who will conduct this procedure?

Personnel

[name]

Personnel

[name]

External User

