Indicate the frequency and duration of visits/sessions as well as the subject's total time commitment for the study.

10-20 minutes for the mentoring group satisfaction survey, 1-2 minutes for each weekly homework survey. Total time commitment: 18-36 minutes

Describe how the data will be collected (i.e. in person or online).

Online through Qualtrics

Will any video, photography, or audio be recorded as part of this procedure?

No

Will data be collected anonymously?

No

Procedure Description

Podcast creation

This procedure is:

Other Procedure

Please explain:

Approximately 10-20 podcasts will be created by [name] and [name] and released during the study time-period. Each podcast will be approximately 15 minutes in duration. Podcasts will contain interviews from content experts related to fathering as well as interviews with fathers interested in being guests. Interviewees will be asked questions about their area of expertise or about their experiences in becoming fathers.

Procedure Description

Podcast dissemination and satisfaction

This procedure is:

Research Activity Involving Participants, Participants Data, or Biospecimens

This procedure is:

Experimental

Where and when will this procedure take place?

Podcasts will be made available to mentoring group participants through a dedicated website maintained by [name] and [name]. DadSpace intervention participants will be invited by their mentoring group facilitator ([name], [name]) to listen to the podcasts as supplementary material to the group program. Podcasts will also be available through public channels (e.g., Apple iTunes, Spotify, etc.) and may be listened to by people who find them spontaneously. Podcast engagement metrics will be evaluated. A link to a brief podcast satisfaction survey through Qualtrics ([name]) will be available on the web page for each podcast episode. Since podcast episodes will be publicly available, a separate online consent form will be used to consent podcast survey participants. Podcast survey participants will be able to complete podcast surveys anonymously and will be invited to enter an email address to be entered into a drawing for an Amazon gift card.

Who will conduct this procedure?

Personnel

[name]

Personnel

[name]

External User

Personnel

[name]

External User

Indicate the frequency and duration of visits/sessions as well as the subject's total time commitment for the study.

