
Recruitment Process

Describe the procedures for identifying and recruiting potential research subjects or requesting pre-existing data or materials.

Participant Group Descriptor

DadSpace Mentoring Group members and wait-listed members

Please describe the recruitment process:

Marketing for the mentoring group will occur through traditional means, such as internet ads/postings, flyers/posters, face-to-face interactions, and email to clinicians and educators in related fields (e.g., pediatricians, OBGYNs, general practice, childbirth educators, doulas). Mentoring group information and sign-up will be available on the WCNC website alongside other class offerings WCNC provides. WCNC will assist in identifying potential subjects through their list of people who have signed up for the mentoring program. Recruitment information will also be available on the WCNC group website. Participants may also be recruited through emails or face-to-face interactions with WCNC staff.

Planned Subject Identification Methods

Direct advertising

Class participants

Referrals

Will a specific agency or institution provide access to prospective subjects?

Yes

Identify Agency

The Women's Clinic of Northern Colorado

Please select the recruitment personnel

[name]

Yes

Please list the external person(s) who will contact prospective students.

Prospective participants will be contacted by [name], [name], and/or [name].

Planned Recruitment Materials/Methods

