***(All advertising must be submitted for review in its final printed/recorded form)**

Note: Attach copies of ALL recruitment materials in the attachment Section

Flyers/posters

Internet ads/postings

Email

Face to face interactions

Is there any possibility that potential participants may feel coerced to participate?

No

Is there any possibility that potential participants may feel undue influence to participate?

No

Participant Compensation/Costs

Will participants be compensated?

Yes

Form of Compensation

Gift Card/Certificate/Voucher

What is the approximate monetary value?

\$44 for the Intervention surveys, possibility to win \$25 for completing a podcast survey

Describe the remuneration plan.

Subjects will be paid for each survey they complete according to the following payment plan: \$8 outcome survey 1 \$10 outcome survey 2 \$10 outcome survey 3 \$10 outcome survey 4 \$6 mentoring group satisfaction survey

Subjects who complete podcast satisfaction surveys will be entered into a drawing each month to win one of two \$25 Amazon gift cards.

Will a 1099 be issued?

No

Will participants incur any costs to participate in this research?

Yes

Explain. This should be clearly outlined in the consent form.

Study participants will all have signed up to participate in the DadSpace mentoring program at the Women's Clinic of Northern Colorado. As with other classes WCNC offers, there is a fee to participate in the program. Class fees have not yet been set, but classes of similar length at The Women's Clinic run \$90.

Risks and Benefits

Minimal risk "means that the probability and magnitude of harm or discomfort anticipated in the research are not greater in and of themselves than those ordinarily encountered in daily life or during the performance of routine physical or psychological examinations or tests." [Department of Health and Human Services 45 CFR 46.102(j)]

Please indicate the researchers' evaluation of the overall risk level, and describe all known risks or discomforts associated with the study procedures, as prompted below. Note that any risks identified here should be consistent with risks you will disclose to participants in the consent process.

Minimal Risk

Are there risks associated with physical well-being?

No

Are there risks associated with psychological well-being?

Yes

Please describe.

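### The SAP names no pretest or posttest survey, and on the schedule the protocol implies, no survey pairs a completed program with an untreated control at equal elapsed time

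*Protocol*

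**What the plan says.** **SAP, Statistical Design and Power.** The plan expects 28 program completers and 28 wait-list controls, each with a pretest and a posttest, analysed by a time-by-group repeated measures ANOVA with two levels of each factor. Exploratory correlations use gain scores from the same pair of tests. The SAP does not mention that there are four surveys.

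**Protocol, Online Surveys.** Mentoring-group fathers and those "who are on a waiting list for the next mentoring group" are surveyed at "four time points over four months, with four weeks between each survey". Clinic staff "will send out a survey link to consented participants at each time point". No survey is labelled pretest or posttest. The event that triggers survey 1 and the length of the control wait are not given.

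**Protocol, Participation in the Mentoring Program.** "Programs will start running in August, 2021, with a new group starting each month". Each program is "1.5 hours per session, with 8 total sessions. Total time: 12 hours".

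**Protocol, Mentoring Program Satisfaction Surveys.** The time budget is "1-2 minutes for each weekly homework survey. Total time commitment: 18-36 minutes", on top of 10-20 minutes for the satisfaction survey. That survey goes only to attendees and is paid separately from the outcome surveys, so it does not define the posttest.

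**Protocol, Recruitment Process and Participant Compensation/Costs.** The participant group is "DadSpace Mentoring Group members and wait-listed members", and "Study participants will all have signed up to participate in the DadSpace mentoring program". Controls are therefore future attendees.

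**The concern.** A wait-list arm is an untreated comparator only while its members are still waiting. If the wait is shorter than the program, controls begin treatment before the program arm finishes, and the comparison the SAP describes has no matching pair of surveys.

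Objective 2 of Study 1 (short-term outcomes of the mentoring program) is labelled primary, and this ANOVA is its only stated between-arm analysis. While the surveys remain unnamed, contrasts with different meanings stay available after the data are seen, and a half-program effect could be reported as the effect of completing the program. The gain-score analyses inherit the same gap.

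**Working it through.** **Inputs**

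- Sessions are weekly: 10 + 8×1 = 18 and 20 + 8×2 = 36 minutes, matching the protocol's total, so there are eight weekly questionnaires for eight sessions. Sessions fall on days 0, 7, ..., 49 of a group.
- Wait (inferred from monthly starts and controls waiting for the next group): groups starting on the same date each month from August 2021 to July 2022 are 28, 30 or 31 days apart. Groups starting on the same weekday of the month are 28 or 35 days apart. The range is 28-35 days.
- Surveys four weeks apart: days 0, 28, 56 and 84 from survey 1.
- Assumption: survey 1 has the same anchor in both arms.

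**Sessions received.** Count the k in 0..7 for which (group start + 7k) is earlier than the survey day. With survey 1 at the index group's start:

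| Control wait | Survey 1 | Survey 2 | Survey 3 | Survey 4 |
|---|---|---|---|---|
| 28-31 days | 0/0 | 4/0 | 8/4 | 8/8 |
| 35 days | 0/0 | 4/0 | 8/3 | 8/7 |
| 49 days | 0/0 | 4/0 | 8/1 | 8/5 |
| 56 days | 0/0 | 4/0 | 8/0 | 8/4 |

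(program/control)

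**Why no placement of a common survey 1 helps.** First to last session takes 7×7 = 49 days. With a wait of at most 35 days, controls start at least 49 − 35 = 14 days before the program arm's last session.

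**Moving the anchor.** Suppose the program arm's first session falls after survey 1 by some lead. Before controls start, the program arm can have had at most the wait divided by 7, rounded up: 28/7 = 4, or 35/7 = 5.

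- Leads of 0, 7, 14 and 28 days: at surveys where controls have had no session, the program arm has had at most 4, 3, 2 and 4 sessions.
- Lead of 21 days with a 35-day wait: by survey 3 (day 56) the program arm has met on days 21, 28, 35, 42 and 49, and controls start on day 56. That is 5/0, the maximum.

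Every one of these is mid-program.

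**Contrasts left under a wait of about a month (survey 1 at the index start)**

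- Program survey 3 against control survey 2: 8 weeks of change against 4, so program effect and time are mixed.
- Survey 3 in both arms: controls have had 3 or 4 of 8 sessions.
- Survey 2 in both arms: treated against untreated at equal time, after 4 of 8 sessions.

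**The SAP's power figure.** With f = d/2 and λ = f²·N·m/(1 − r), d = .50 gives λ = .25² × 56 × 2/.5 = 14.0. On F(1, 54), with alpha .05 two-sided assumed because the SAP states none, power is .957, which reproduces the stated .95. On this formula d = .50 is a 1.0 SD difference in change: the standard error of that difference is √(2×(1 − .5))×√(2/28) = .267 SD, and √14.0 × .267 = 1.0. If half the effect were present at the chosen contrast (an assumption; the documents give no accrual figure), the difference is 0.5 SD, λ = 3.5 and power is .451.

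**The case against.** The strongest reply is that the SAP's wording already settles the matter: program fathers are tested after completing the program, and controls are tested while still on the wait list. That is the plain reading, and it makes a week 4 contrast a departure from the SAP. It does not rescue the plan under a one-month wait, because it then forces program week 8 against control week 4. A reader might infer that the SAP has chosen that unequal comparison; it has not, since it names no survey.

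Second, the wait and the anchor are inferred. Consent follows sign-up, so a control surveyed from sign-up at least eight weeks before his own group would be untreated at survey 3. The grant proposal, the consent form, the measures file and the section 4.2 that the SAP cites are not reproduced and could set the timing. This stands, and it makes the consequence conditional. It does not touch the fact that no survey is named.

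Third, this is a feasibility pilot. That is fair for Objective 1, which is unaffected. Objective 2 is also labelled primary, and the SAP claims power .95 for it.

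The mismatch between four months and three four-week gaps (12 weeks) is loose wording and carries no weight here.

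**Conclusion.** The concern holds in two parts. Without condition: neither document says which of four surveys is the pretest or posttest in either arm. On condition of weekly sessions, a common survey 1 anchor and a control wait of 28-35 days: no survey compares a completed program with an untreated control at equal elapsed time. The program arm has had at most 5 of 8 sessions wherever controls have had none, and 4 of 8 if survey 1 is at the index group's start.

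With survey 1 at that start, the condition fails once controls wait 56 days. The exact figure moves with the anchor, but it must exceed the 49 days from first to last session.

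Two stronger readings are tempting. One is that the design cannot show any program effect. The documents do not support that: survey 2 in both arms is a valid comparison for part of the program, and a longer wait may have been intended. The other is that true power is .45. That figure rests on an assumed half accrual and only illustrates the sensitivity.

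**What to change.** Before data are seen:

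1. In the SAP, name the pretest and posttest survey for each arm. Require equal elapsed time in both arms and a control posttest before the control group's first session. Use the same definition for the gain scores.
2. State what anchors survey 1 and how long controls wait. Reconcile the protocol's program schedule and survey schedule with the SAP's completed-program comparison, and tidy the four-month wording.
3. If the wait is about a month, the qualifying posttest is the last survey before the control group's first session (survey 2 if survey 1 is at the index group's start). Report the result as a partial-program effect, giving the number of sessions received, and not as the effect of completing the program.

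The cost is SAP and protocol wording, with no added surveys. If the wait is about a month, the price is a narrower estimand than the SAP now describes. If a full-program contrast is wanted, the schedule has to provide an untreated control posttest at the same elapsed time as the program posttest. That is only a clarification if a longer wait was already intended; otherwise it is a design change for the investigators to weigh. A staggered-start model on all four surveys, response windows and late-responder analyses are optional.

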Where and when will this procedure take place?

Participants will be recruited from the pool of people who have signed up for the mentoring group through WCNC. WCNC will advertise the mentoring group through their website and marketing materials as they do for other education classes they offer. Fathers who sign up for or express interest in the group program will be provided information about the associated research study by information posted on the WCNC website or by WCNC staff through verbal interaction, emails and/or flyers handed out at the clinic. Social media (e.g., Instagram/Facebook) postings made by department and clinic accounts will also be used to promote the study. Participation in the study is not required for those attending the mentoring group. Fathers attending the mentoring groups will be provided with links to listen to podcast episodes. Podcast listeners who have consented to participate in the study will be invited through the podcast website to complete brief satisfaction surveys about each podcast episode using their study ID.

Who will conduct this procedure?

Personnel

[name]

External User

Personnel
[name]

External User

Personnel
[name]

External User

Indicate the frequency and duration of visits/sessions as well as the subject's total time commitment for the study.

Describe how the data will be collected (i.e. in person or online).

Sign-ups for mentoring groups will occur online through the WCNC website.

Will any video, photography, or audio be recorded as part of this procedure?

No

Will data be collected anonymously?

No

Procedure Description
Screening and Consent

This procedure is:

Research Activity Involving Participants, Participants Data, or Biospecimens

This procedure is:

Where and when will this procedure take place?

All those who have decided to take part in the mentoring groups will be assigned an ID by WCNC staff. Potential participants will use this ID to complete an online screener survey. Those who are eligible will then be automatically provided consent information online through Qualtrics. Research staff will notify WCNC staff of the ID numbers of consented participants for management of survey distribution.

Who will conduct this procedure?

Personnel

[name]

Personnel

[name]

External User

Indicate the frequency and duration of visits/sessions as well as the subject's total time commitment for the study.

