~15 minutes for each podcast, up to 20 podcasts. Total possible time for listening: 5 hours The podcast survey will take approximately 1-5 minutes.

Describe how the data will be collected (i.e. in person or online).

Podcast engagement metrics will be collected online through the podcast website. Podcast satisfaction surveys will occur online through Qualtrics.

Will any video, photography, or audio be recorded as part of this procedure?

No

Will data be collected anonymously?

Yes

Procedure Description

Data Analysis

This procedure is:

Research Activity Involving Participants, Participants Data, or Biospecimens

This procedure is:

Experimental

Where and when will this procedure take place?

Analysis of study data will occur at CSU by members of the research team.

Data will be monitored throughout the study collection period to monitor for any adverse events. Data analysis will occur at the end of the study collection period. Only aggregated data outcomes without identifiers will be provided to staff at the women's clinic.

Who will conduct this procedure?

Personnel

[name]

Personnel

[name]

Personnel

[name]

Indicate the frequency and duration of visits/sessions as well as the subject's total time commitment for the study.

N/A

Describe how the data will be collected (i.e. in person or online).

N/A

Will any video, photography, or audio be recorded as part of this procedure?

No

Will data be collected anonymously?

No

Procedure Description

Following up with participants about potentially concerning survey responses

This procedure is:

Research Activity Involving Participants, Participants Data, or Biospecimens

This procedure is:

Standard of Care or Established Practice

Where and when will this procedure take place?

Should participants list high scores on measures of depression or anxiety or indicate in survey responses ideation about self harm, research staff ([name]) will contact staff at WCNC ([name]) to notify them of a participant who may need additional support. WCNC staff will reach out to the participant to provide referral resources as needed.

Who will conduct this procedure?

Personnel

[name]

Personnel

[name]

External User

Indicate the frequency and duration of visits/sessions as well as the subject's total time commitment for the study.

N/A

Describe how the data will be collected (i.e. in person or online).

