Identifiable information will only be accessible to WCNC staff. WCNC staff will provide ID numbers to each participant to use for completing their surveys. Research staff will only have access to participant ID numbers paired with survey data, not participant names or contact information. Survey responses will be aggregated for the purposes of reporting to community partners, stakeholders, publications, and grant reports. Given the small sample size, it is possible a person's data could be linked to their demographic information. To mitigate this risk, any data reported by demographic will be withheld if the demographic subgrouping contains a population of 3 or fewer people.

Clinical Trial

Will participants will be prospectively assigned to one or more interventions (including placebo or other control)?

Yes

Will the study evaluate the effects of the intervention on health-related outcomes (biomedical or behavioral)?

Yes

Does this study involve an FDA-regulated drug or device?

No

Will the study be conducted as a
Single-Site Clinical Trial

Will this study be posted on ClinicalTrials.gov?

Yes

ClinicalTrials.gov Registration# (or pending)

Pending

Additional information and support available through CSU Quality Assurance:

[contact]

Participant Population

Are you interacting or intervening with participants?

Yes

Provide an estimate of the anticipated participant total.

56

Are you analyzing existing data records or biospecimens?

No

Inclusion and Exclusion Criteria (e.g., Participants must have 20/20 vision, Participants must be 30-45 years of age, etc.) This should match your screening, consent, and recruitment materials.

Please list all inclusion criteria

Participants must be expecting a baby or have a baby less than one year of age and have signed up to participate in the DadSpace mentoring program at WCNC

Please list all exclusion criteria

Less than 18 years of age, non-English-speaking.

What is the rationale for studying the requested group(s) of participants?

These participants comprise the target population of people served by the clinic and the primary focus of the intervention.

Will you use a screening procedure, instruments, tools, questionnaires etc.?

Yes

Describe any planned screening procedures. Attach your screening document(s) (e.g., health history questionnaire), if applicable at the end of the form.

Participants will be screened for inclusion and exclusion criteria as listed above. Screening questions are attached.

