[Data Management Services at CSU Libraries](#)

[General guidance and unfunded projects](#) (DMPTool)

[Funder-specific guidance and templates](#) (DMPTool)

If you choose to create a standalone data management plan (DMP) for your own purposes or at the direction of a funding agency, please attach that document to your protocol, also.

A [DMP fillable template](#) is available from CSU Libraries.

How will the data be stored and backed up during the research?

Initially, data will be managed and stored on Co-PI [name]'s password-protected Qualtrics account. Data will be downloaded from Qualtrics to a password-protected file folder in a secure HDFS research drive for statistical analyses (e.g., SPSS, Mplus). Access to this folder will only be granted to study personnel. Both Qualtrics and the PI's personal account are secure storage systems that are backed up regularly. A metadata repository will be developed for each study that describes the source of the data, a codebook for the demographic questions, syntax for computation of scale scores, and types of data files available (e.g., Excel, SPSS).

Who will be responsible for data and access management, and security?

Data Access Responsibility

[name]

Data Access Responsibility

[name]

Data Access Responsibility

[name]

Who will have access to study records or specimens?

Personnel

[name]

Personnel

[name]

Personnel

[name]

Will any external personnel have access to study records or specimens?

Yes

Please identify the external personnel with access to study records/data

WCNC staff ([name], [name], and [name]) will have access to participants' contact information and associated participant ID numbers. They will not have access to research data (survey data) associated with each participant ID.

How will you share the data?

Data outcomes will be reported in aggregate through reports to stakeholders and manuscripts. The availability of the data sets will be communicated to research peers and at conferences, and referenced in publications. The embargo period for the data sets restricting public access will be for two years from completion of the studies, and will be implemented in CSU's Digital Repository. Afterward, materials will be made available via persistent URLs configured for discovery by all major web crawlers.

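### Survey linkage and self-harm alerts both rest on an ID that each father enters himself, and the supplied text describes no check or reconciliation of it

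*Protocol*

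**What the plan says.** **Linkage.** Under Procedures, Online Surveys, fathers in the mentoring group or on its waiting list "will be invited to complete electronic surveys at four time points over four months, with four weeks between each survey". A clinic staff member "will send out a survey link to consented participants at each time point", and "Participants will enter their unique ID number in each survey so surveys can be linked over time". The application form appears twice in the protocol file, and both copies read the same. Under Screening and Consent, "Potential participants will use this ID to complete an online screener survey"; research staff then tell the clinic which IDs have consented.

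**Who holds what.** Under Privacy and Confidentiality: "Research staff will only have access to participant ID numbers paired with survey data, not participant names or contact information". In the data management answers, named clinic staff "will have access to participants' contact information and associated participant ID numbers", but "They will not have access to research data (survey data) associated with each participant ID".

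**Alerts.** If a survey shows high depression or anxiety scores or thoughts of self-harm, research staff notify the clinic, and "WCNC staff will reach out to the participant to provide referral resources as needed".

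**Analysis.** The SAP plans a 2 (time) by 2 (group) repeated measures ANOVA on 28 program fathers and 28 wait-list fathers with both pretest and posttest. The protocol's anticipated total is also 56.

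**The concern.** A key that respondents enter by hand, repeatedly and over months, will sometimes be wrong. Here the same key does two jobs.

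First, it joins pretest to posttest. An entry that matches nobody breaks the pair, and the SAP's test needs both halves. An entry that matches another father mixes two men's records and gives a false change score, which no missing-data method would notice. Because the anticipated total equals the number of completers required, there is no reserve.

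Second, it carries the safety hand-over. Research staff have no names, so they can pass on only the ID that came with the answers. If that ID matches no issued ID, the alert identifies no father. If it matches another issued ID, the clinic may contact the wrong man. Either way, the father who gave the answer may not be reached.

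**Working it through.** **1. The SAP's power figure as baseline.** Inputs from the SAP: d = 0.50, stability r = 0.50, N = 56, two time points (m = 2). Alpha is not stated; 0.05 is assumed. For the group-by-time interaction with f = d/2 = 0.25:

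λ = f² × N × m / (1 − r) = 0.0625 × 56 × 2 / 0.50 = 14, on 1 and 54 degrees of freedom. Power = 0.957, which reproduces the stated .95.

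**2. Pairs lost.** Let e be the chance that an entered ID is wrong and stays unrepaired. The documents give no rate, so 1%, 2% and 5% are assumptions. With independent errors, a pre/post pair fails with probability 1 − (1 − e)². Retained N = 56 × (1 − e)², and λ = 0.25 × N.

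| e | pairs broken | fathers lost of 56 | N left | power, d = 0.50 | loss in points |
|---|---|---|---|---|---|
| 0 | 0 | 0 | 56 | 0.957 | – |
| 1% | 2.0% | 1.1 | 54.9 | 0.953 | 0.4 |
| 2% | 4.0% | 2.2 | 53.8 | 0.949 | 0.8 |
| 5% | 9.8% | 5.5 | 50.5 | 0.936 | 2.1 |

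If an analysis needed all four surveys, the exponent would be 4, N would be 53.8, 51.7 or 45.6, and power 0.949, 0.941 or 0.910. The SAP's test needs only two.

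These losses use the SAP's own effect-size convention. If d = 0.50 instead meant the between-group difference in change, a normal approximation puts power at 0.46 before any loss and 0.457, 0.450 or 0.428 after it. That lowers the level of power, but linkage loss is still not the main problem.

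**3. Will errors occur at all?** Pre and post together make 56 × 2 = 112 entries. The chance of at least one wrong entry, 1 − (1 − e)^112, is 0.68 at 1%, 0.90 at 2% and 0.997 at 5%.

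**4. Alerts.** The protocol does not say how many alerts to expect or define a high score. As an illustration only, its Background cites perinatal depression in about 13% of fathers: 0.13 × 56 = 7.28, about 7. If each gave rise to one alert, the chance that at least one carried a wrong ID, before any repair, would be 1 − (1 − e)^7 = 6.8%, 13.2% or 30.2%. How many of those would match another issued ID depends on the ID format, which is not given, so no figure can be put on contact with the wrong father.

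**5. Detection and repair, from the text.** Research staff can see an ID that is not on the consented list, two records under one ID in a wave, or a consented ID with no record. They cannot see whose record it is. The clinic can translate an ID into a man but cannot see the answers. Repair needs both sides, and the supplied text gives no procedure for it.

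**The case against.** A reader might infer that nobody can detect or repair a wrong ID. The documents do not support that. Research staff hold the list of consented IDs, and duplicates and gaps within a wave are visible. The surveys collect demographics, which give a second matching key. Fathers are paid per survey, so completion has to be traced to individuals, and an unpaid father has reason to ask. The plan is silent on repair; it does not exclude it. The data management plan, screener and survey measures are listed as attachments but are not in the supplied text, and any of them might describe entry checks.

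A reader might also compound the error rate over every form a program father completes, including the weekly homework questionnaires and the satisfaction survey. That would measure neither harm: those forms are not part of the pre/post pair, and they are not described as carrying the mental health measures.

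Most of this stands, and it limits the point to what is not described. Three things remain:

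- The consented list may itself inherit an error, because fathers use the ID at the screener. That they type it there is the natural reading, but the text does not say so.
- Matching on demographics would mean passing individual survey data to the clinic or names to research staff, which the separation of roles is meant to prevent.
- An entry equal to another issued ID need not appear as unmatched, and it shows as a duplicate only if the other father answers in the same wave.

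Individual links have a risk of their own: a link sent to the wrong man files a whole record under the wrong ID with nothing to show it.

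**Conclusion.** The concern holds in a limited form. One self-entered ID is the only described key for linkage and for tracing an alert, and the supplied text describes neither a check on entry nor a reconciliation route. The effect on the analysis is small: about 1 to 5 of 56 fathers and 0.4 to 2.1 points of power. That rests on assumed, independent, unrepaired error rates of 1% to 5%, alpha 0.05, and the SAP's convention for d. Informal repair would make the loss smaller; records mixed between two fathers would do harm that the table does not count.

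The alert route carries the point. Its consequence is serious, its frequency cannot be estimated from the documents, and the remedy is cheap. It is a change that should be made, but not one on which the primary analysis depends.

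**What to change.** In both copies of Online Surveys, replace "Participants will enter their unique ID number in each survey so surveys can be linked over time" with wording such as: *Each consented participant will receive an individual survey link that carries his study ID as embedded data, so that surveys can be linked over time without the participant entering the ID.* The clinic staff member who already sends the links would send each father his own, and the screener link should work the same way. Research staff still see no names. Check in the set-up that holding these links gives clinic staff no view of the answers.

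If fathers must go on entering the ID, issue non-sequential IDs with a check digit and validate it on entry.

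In either case, add a short written procedure: after each wave, research staff and the clinic reconcile unmatched, duplicate and missing IDs by ID alone, exchanging neither answers nor names. The procedure should also cover alerts and state who resolves an alert whose ID cannot be matched. If the attached data management plan already covers this, a cross-reference is enough.

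The cost is a one-off survey set-up and a few sentences in the protocol. The continuing burden is that clinic staff send individual links and check that each goes to the right father.
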